#### **8.5.2 Time to mechanical ventilation, hospital discharge and overall survival**

Time to mechanical ventilation is defined as the time from randomization until mechanical ventilation (i.e. date of mechanical ventilation or censoring – date of randomization + 1). Any patient not known to have initiated mechanical ventilation at the time of analysis will be censored based on the last recorded date on which the patient was known to not requiring

mechanical ventilation (e.g. date of Day 15 visit, date of early discontinuation, or date of death). A separate analysis of time to IMV *or* ECMO will also be conducted with the same definition as above, but both IMV and ECMO will be considered as an event.

Overall survival is defined as the time from randomization until death (i.e. date of death or censoring – date of randomization + 1). Any patient not known to have died at the time of analysis will be censored based on the last recorded date on which the patient was known to be alive.

Time to hospital discharge is defined as the time from randomization until hospital discharge (i.e. date of hospital discharge or censoring – date of randomization + 1). Any patient not known to have been discharged at the time of analysis will be censored based on the last recorded date on which the patient was known to be hospitalized (e.g. date of visit, date of early discontinuation, or date of death).

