## 6 Sample size determination

The study will enroll a total of 54 patients, 18 per arm according to the 1:1:1 randomization.

The sample size has been estimated based on the following assumptions:

- An overall one-sided significance level for efficacy of 0.097 (9.7%) and a power of 74% for each comparison under the assumption that the true success rates are 50% in the SoC group increasing to 80% in the emapalumab or anakinra groups.
- The study will consist of two stages. The Stage 1 interim analysis will be conducted after the accrual of at least 9 patients per treatment arm.
- There is the potential to stop for futility or for efficacy of emapalumab or anakinra (or both) at the end of Stage 1, but only the futility rule is binding and irrespective of the Stage 1 results, the study will not be stopped for efficacy but continue to accrue efficacy and safety data.

The value for the type I error has been chosen in recognition of the urgent unmet medical need to allow the identification of a signal, at least, from a statistical perspective. Having seen a statistical signal, it is then a matter of evaluating whether the observed treatment differences represent clinically relevant effects that can satisfy that unmet need. Assuming no untoward safety signal is observed and no futility stopping occurs at the Stage 1 interim, the decision may be taken to increase the sample size beyond 54 patients in order to accrue further safety and efficacy data. Details of this would be described in a protocol amendment. In case the outcome is statistically convincing, i.e. statistically significant on a 5% level in the stage 2 analysis, efficacy will be considered confirmed and the results may be used to seek regulatory approvals. The DRC will provide support in such discussions.

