### **8.5 Derived and computed variables**

#### **8.5.1 Treatment success**

Treatment success is achieved for patients not requiring IMV or ECMO by Day 15. If IMV or ECMO is required at any visits prior to Day 15/date of early discontinuation, but no longer required at Day 15/date of early discontinuation, treatment success has been achieved. If IMV or ECMO is not initiated during the study, treatment success has been achieved. As stated in Section 8.2.1, patients who discontinue study treatment (or discontinue the study if randomized to standard of care) prior to Day 15 and had ECMO or IMV on their last assessment by the time of study treatment discontinuation, will be considered not having achieved treatment success by Day 15. Patients who discontinue prior to Day 15 without ever having initiated IMV/ECMO, have achieved treatment success by Day 15. Patients discontinuing prior to Day 15 due to having significantly improved will be considered having achieved treatment success. Patients who died by Day 15, have not achieved treatment success regardless of IMV/ECMO use by Day 15.

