### 12.2.1 Time to mechanical ventilation, hospital discharge and overall survival

Analysis of the time to mechanical ventilation from the point of randomization will be undertaken by plotting Kaplan-Meier curves for each of the 3 treatment groups and by pairwise comparisons (emapalumab/anakinra versus standard of care) using the log-rank test. Hazard ratios will be estimated using the Cox proportional hazards model and these will be presented together with 90% two-sided confidence intervals. Time to IMV *or* ECMO will be analyzed using the same approach.

Overall survival (time to death from the point of randomization) and time to hospital discharge (from the point of randomization) will not be analyzed at the end of Stage 2, but at the end of the follow-up period. This endpoint will be analyzed as for time to mechanical ventilation.

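### Time to mechanical ventilation and time to IMV or ECMO censor at death; add a composite with death and a cumulative incidence plot

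*SAP*

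**What the plan says.** **Censoring.** Under SAP 8.5.2, a patient not known to have been ventilated is censored on the last date known not to require "mechanical ventilation (e.g. date of Day 15 visit, date of early discontinuation, or date of death"). The SAP adds a separate analysis of time to IMV or ECMO "with the same definition as above, but both IMV and ECMO will be considered as an event", so death is censored there too.

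**Primary endpoint.** SAP 8.5.1 states: "Patients who died by Day 15, have not achieved treatment success regardless of IMV/ECMO use by Day 15". SAP 8.2.1 and Protocol 7.3.8 carry the same rule.

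**Analysis.** SAP 12.2.1 states: "Analysis of the time to mechanical ventilation from the point of randomization will be undertaken by plotting Kaplan-Meier curves". It adds pairwise log-rank tests, and "Hazard ratios will be estimated using the Cox proportional hazards model and these will be presented" with 90% two-sided intervals. Protocol 7.3.3.2.1 specifies the same methods for time to mechanical ventilation. Time to IMV or ECMO appears only in the SAP.

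**Death on its own.** "Overall survival is defined as the time from randomization until death" (SAP 8.5.2). Protocol 7.3.3.2.1 and SAP 12.2.1 defer that analysis to the end of follow-up. Death is also category 1 of the exploratory 7-point scale.

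**Not planned.** Neither document describes a composite of IMV, ECMO or death, a cumulative incidence analysis, or a sensitivity analysis of the censoring rule.

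**The concern.** A patient who dies without being intubated leaves the ventilation analysis as a censored observation, just like a patient who was still well when last seen. The primary analysis scores that patient as a failure. Ventilation is an unfavourable event, so death before intubation removes patients who can no longer have it. If one arm has fewer intubations because some of its sickest patients died first, the curve, log-rank test and hazard ratio can point towards benefit where overall failure shows none.

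Death before intubation is plausible here. Patients aged up to just under 85 are eligible (Protocol 5.3.1), and the rationale in Protocol 3.1 is pressure on access to intensive care. Time to mechanical ventilation is the first-listed secondary endpoint, and SAP 2 foresees use of the planned analyses in regulatory submissions and manuscripts.

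**Working it through.** **The plan's own figure.** The documents give no operating characteristics for the ventilation analyses. The only power figure is for the primary test: "An overall one-sided significance level for efficacy of 0.097 (9.7%) and a power of 74% for each comparison", assuming "the true success rates are 50% in the SoC group increasing to 80% in the emapalumab or anakinra groups" (SAP 6). Exact enumeration of the two-stage Fisher design (9 then 18 per arm; boundaries 0.690, 0.025 and 0.159) gives 73.6%, which agrees with 74%. The check below takes 18 per arm and 50% failure on standard of care (SoC) from that section.

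**Assumption.** Let F be the Day 15 failure probability in an arm, and s the share of failures that are deaths before IMV. The documents give no s, so it is varied.

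**Formulas (constant hazards, Day 15 horizon).**
- Total hazard = -ln(1 - F)/15. With F = 0.50 this is 0.6931/15 = 0.0462 per day.
- Ventilation hazard = (1 - s) × total hazard.
- Hazard ratio (HR), active vs SoC, death as an event = ln(1 - F_active)/ln(1 - F_SoC).
- HR, death censored = that ratio × (1 - s_active)/(1 - s_SoC).

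**Lead case.** SoC 40% IMV + 10% death gives s = 0.2. Active 20% + 30% gives s = 0.6. Both have F = 0.50. Censored HR = 0.4/0.8 = 0.50; with death as an event, 1.00.

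**Converse case.** SoC 30% + 20% gives F = 0.50 and s = 0.4. Active 20% + 0% gives F = 0.20 and s = 0. HR with death as an event = 0.2231/0.6931 = 0.32. Censored HR = 0.32 × 1/0.6 = 0.54.

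The last two columns give the share of simulated trials (18 per arm) with one-sided log-rank p < 0.05 favouring active. Ranges come from two independent runs of 4,000 to 6,000 trials. The equal-split row is from one run of 4,000.

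| SoC vs active (IMV + death without IMV) | HR, death censored | HR, death as event | p < 0.05, censored | p < 0.05, death as event |
|---|---|---|---|---|
| 40% + 10% vs 40% + 10% | 1.00 | 1.00 | 5% | 5% |
| 40% + 10% vs 30% + 20% | 0.75 | 1.00 | 12–13% | 5% |
| 40% + 10% vs 20% + 30% | 0.50 | 1.00 | 29–30% | 5% |
| 30% + 20% vs 20% + 0% | 0.54 | 0.32 | 23–25% | 61–62% |

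With equal total failure and no such deaths on SoC, the censored HR is 1 - s_active: 0.9, 0.8, 0.7, 0.6 and 0.5 for shares of 10% to 50%.

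**Constructed data.** Take 18 vs 18, with 9 failures per arm on the same days and all SoC failures being IMV. If 2, 3, 4 or 5 active failures are deaths instead of IMV, the censored HR is 0.78, 0.67, 0.56 or 0.44. With death as an event it is 1.00 each time. If active has 4 IMV + 6 deaths (8/18 successes against 9/18), the censored HR is 0.44 (90% CI 0.17–1.19), against 1.11 (0.52–2.37) with death as an event.

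**Where the reversal does not occur.**
- With equal intubation hazards and the active death hazard multiplied by 1, 3 and 6, one-sided p < 0.05 favours active in 5.2%, 5.1% and 4.9% of simulated trials.
- With 9 IMV + 4 deaths against 9 IMV, the censored HR is 1.19, against 1.71 with death as an event. Harm is understated, but the arm does not look protective.

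**Kaplan-Meier level.** In the lead case, 1 - KM with death censored is 1 - 0.5^0.8 = 42.6% on SoC (true 40%) and 1 - 0.5^0.4 = 24.2% on active (true 20%). In the 9 IMV + 4 deaths example it is 58.4%, against an observed 9/18 = 50%.

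**The case against.** **A cause-specific hazard ratio is a legitimate quantity.** This stands. In the lead case the active arm really does have half the intubation hazard and three times the hazard of death before intubation. The 29–30% is therefore power for a real difference in one component, not a false-positive rate. But the SAP does not label the ratio as cause-specific and sets nothing beside it that includes death.

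**The endpoint is what its name says, and it is secondary.** This also stands. Time to ventilation is a different quantity from treatment success. Protocol 7.3.1 makes secondary endpoints descriptive and their p-values exploratory. The primary Fisher test already counts the deaths.

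**Deaths are visible elsewhere.** Partly right. They enter the primary endpoint, the 7-point scale, the listings and overall survival. In the lead case the active arm had more unventilated deaths in 91% of simulated trials, so the imbalance would usually be seen. But the overall survival analysis is deferred to the end of follow-up, so it is not available beside the ventilation analyses at Stage 2.

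**Tempting stronger reading.** A reader might infer that the rule always favours the arm with more unventilated deaths. It does not: with equal intubation hazards there is no tilt, and extra deaths on top of unchanged intubations only hide or understate harm.

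**Conclusion.** The concern holds in a limited form. Both ventilation analyses censor at death, the primary endpoint counts death by Day 15 as failure, and nothing planned for Stage 2 combines ventilation and death over time. If deaths displace intubations, equal total failure can appear as a hazard ratio of 0.75 or 0.50. In the converse case, where active treatment prevents deaths before intubation, power falls from 61–62% to 23–25%. These sizes rest on assumed splits, constant hazards and 18 per arm. With the same split in both arms there is no distortion of the hazard ratio. Whenever some deaths precede ventilation, 1 - KM overstates the real probability of ventilation.

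Two further inferences are not supported. First, the primary conclusion is not at risk, because the Fisher test is unaffected. Second, disagreement between the primary result and these analyses need not come from deaths. SAP 8.5.1 counts a patient ventilated earlier but off IMV/ECMO at Day 15 as a success, while SAP 8.5.2 counts the same patient as an event. This is a change that should be made, not one on which the trial's validity depends.

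**What to change.** In SAP 8.5.2 and 12.2.1:

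1. Add time to IMV, ECMO or death, analysed by log-rank and Cox and reported at Stage 2, alongside the two existing analyses.
2. Plot time to mechanical ventilation also as cumulative incidence with death as a competing event.
3. Keep the Kaplan-Meier, log-rank and Cox analysis that Protocol 7.3.3.2.1 specifies, and label its hazard ratio as cause-specific. Removing or demoting that analysis would depart from the protocol and is not needed.
4. State that the composite is closer to the primary endpoint but not an exact counterpart, because patients off IMV/ECMO by Day 15 count as primary successes.

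The cost is SAP text, one extra analysis and one extra plot. No new data are needed: dates of IMV and ECMO are recorded (Protocol 5.5.3.1), survival is collected (Protocol 5.5.3.8), and the SAP already uses the date of death for censoring and overall survival.

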5.4.5 Selection and timing of doses for each patient

5.4.5.1 Emapalumab

Emapalumab will be administered by intravenous (i.v.) infusion over a period of 1 to 2 hours depending on the volume to be infused, at an initial dose of 6 mg/kg.

Emapalumab treatment will be continued at the dose of 3 mg/kg, every 3rd day until Day 13 i.e., Days 4, 7, 10 and 13. The following information will be recorded in the CRF for each emapalumab administration: date, start and end time, total dose infused, and, if infusion was interrupted, reason for interruption.

Emapalumab must be prepared by a Pharmacist or other appropriately qualified staff member, specifically authorized by the Investigator/Pharmacist and appropriately licensed to perform the task.

The specific dose to be administered for an individual infusion will be determined based on the patient's body weight at screening.

Full instructions for the preparation of emapalumab, including dilution steps and method for administration, are available in the IMP manual.

The patient should receive the designated volume of the infusion material through an infusion pump over 1 to 2 hours depending on the volume to infuse. A 0.2 μ m filter must be included in all infusion lines.

It is recommended that an i.v. central line remains in place to ensure venous access during the treatment period.

Since no data are available on the compatibility of emapalumab with other i.v. substances or additives, other medications/substances should not be added to the infusion material or infused simultaneously through the same i.v. line. If the same i.v. line is used for subsequent infusions of other drugs, the line should be flushed appropriately with saline before and after infusion of emapalumab.

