5.4.5.2 Anakinra

Anakinra will be administered by i.v. infusion at total dose of 400 mg per day, divided in 4 doses 100 mg i.v. every 6 hours.

Anakinra treatment will continue for 15 days i.e., Days 1 to 15. The following information will be recorded in the CRF for each anakinra administration: date, start and end time, total dose infused, and, if infusion was interrupted, reason for interruption.

Before administration, the full content of the prefilled, single-use syringe (anakinra 100 mg) will be diluted in 100 mL saline. The i.v. administration of anakinra has to occur immediately after the preparation over an infusion period of 60 minutes. A particle reduction inline filter will be assembled with the infusion set.

Full instructions for the preparation of anakinra are available in the IMP manual.

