### 3.4.4 Exploratory endpoints

Clinical status assessed by a 7-point ordinal scale. The scale consists of the following categories:

1. Death
2. Hospitalized, requiring invasive mechanical ventilation or extracorporeal membrane oxygenation (ECMO)
3. Hospitalized, requiring non-invasive ventilation or high flow oxygen devices
4. Hospitalized, requiring supplemental oxygen
5. Hospitalized, not requiring supplemental oxygen - requiring ongoing medical care
6. Hospitalized, not requiring supplemental oxygen - no longer requires ongoing medical care
7. Not hospitalized

PK parameters will be calculated for emapalumab and anakinra by non-compartmental analysis and population analysis, as applicable.

PD biomarkers: Change from baseline in CXCL9, IL-1, IL-6, sIL-2R and selected biomarkers relevant for hyperinflammation.

[figure not shown]

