## 4 Study methods

### 4.1 Overall study design and plan

The study consists of screening, a 2-week treatment period and an 8-week follow-up period. The 2-week treatment period is open, and the patients will be randomized to treatment with emapalumab, anakinra or standard of care in a 1:1:1 ratio. Patients will be stratified based on glucocorticoid treatment at randomization to ensure an equal distribution between treatment arms. Emapalumab will be administered as i.v. infusions every 3rd day for a total of 5 infusions (Days 1, 4, 7, 10, 13). Anakinra will be administered as 4-times daily i.v. infusions for 15 days (Days 1 to 15). The primary endpoint will be evaluated at Day 15.

An early follow-up visit will be performed at Day 28. A follow-up by visit or phone call will be performed 4 and 8 weeks after the end of the treatment period (Weeks 6 and 10). The study duration for an individual patient will not exceed 10 weeks. The end of the study is defined as last patient, last follow-up visit/phone call. See Figure 1.

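### Time to hospital discharge may look delayed in the active arms, most for anakinra, to the extent that recovered patients stay in hospital to finish the i.v. course; add a supportive analysis of readiness for discharge.

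*SAP*

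**What the plan says.** SAP 8.5.2: "Time to hospital discharge is defined as the time from randomization until hospital discharge", computed as discharge date minus randomization date plus 1. There is no readiness criterion. SAP 12.2.1 adds "This endpoint will be analyzed as for time to mechanical ventilation", which means Kaplan-Meier curves, pairwise log-rank tests against standard of care, and Cox hazard ratios with 90% two-sided confidence intervals, run at the end of follow-up.

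The arms differ in what they require of a patient who has recovered:

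- **Anakinra** (Protocol 5.4.5.2): "Anakinra treatment will continue for 15 days i.e., Days 1 to 15", "divided in 4 doses 100 mg i.v. every 6 hours", each dose given "over an infusion period of 60 minutes".
- **Emapalumab** (Protocol 5.4.5.1): infusions on Days 1, 4, 7, 10 and 13. "It is recommended that an i.v. central line remains in place to ensure venous access during the treatment period".
- **Standard of care** (Protocol 5.4.1 and 5.4.3): no study drug and no placebo infusions.

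Clinical status is recorded on a 7-point scale at Visits 1 to 9 (Protocol 5.5.5.1). Category 6 is "Hospitalized, not requiring supplemental oxygen - no longer requires ongoing medical care" and category 7 is out of hospital. SAP 12.4.1 only tabulates the scale by category over time.

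**The concern.** The event is a calendar date, and only the active arms have a fixed i.v. course that can outlast the illness. Four one-hour infusions a day are hard to combine with going home. If a recovered patient stays in to complete the course, the endpoint records the infusion schedule rather than recovery. The error runs one way, towards apparent delay on active treatment, and the anakinra course is both longer and denser than the emapalumab course.

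The endpoint is listed among those supporting the primary objective, and its hazard ratio and interval will be reported. A drug with no effect on recovery could appear to lengthen hospital stay, and a real benefit could be masked.

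**Working it through.** The documents give no event count, median, hazard ratio or power for this endpoint, so there is no stated figure to reproduce.

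**One patient.** Randomization is on Day 1 and the patient is ready to leave on Day 8. Under SAP 8.5.2:

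- Standard of care, leaves when ready: 8 − 1 + 1 = 8 days.
- Emapalumab, stays to the last infusion: 13 − 1 + 1 = 13 days (5 more).
- Anakinra, stays to the last day of treatment: 15 − 1 + 1 = 15 days (7 more).

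**Trial level, no drug effect.** Let R be the day of readiness, with the same distribution in both arms. Standard-of-care discharge is R. Anakinra discharge is max(R, 15) for a patient who stays for the course, and R for one who stops early. There are 18 patients per arm (SAP 6), follow-up ends at Day 70, and there are no deaths. The test is two-sided at 10%, which matches the 90% interval. The distribution of R and the share stopping early are assumptions. With R log-normal (log-SD 0.5), the share ready by Day 15 is Φ(ln(15/median)/0.5):

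| Median R (day) | Ready by Day 15 | HR, all stay | Rejection, all stay | HR, half stop early | Rejection, half stop early |
|---|---|---|---|---|---|
| 8 | 90% | 0.30 | 98% | 0.56 | 61% |
| 10 | 79% | 0.47 | 82% | 0.70 | 37% |
| 12 | 67% | 0.63 | 50% | 0.80 | 22% |
| 15 | 50% | 0.79 | 20% | 0.91 | 12% |

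**Which row fits the plan.** Protocol 7.1 and SAP 6 assume 50% success on standard of care. Under SAP 8.5.1, failures are essentially patients on invasive ventilation or ECMO at Day 15 or at early discontinuation, or dead by Day 15. None of these is ready for discharge. With no drug effect, about half of each arm is therefore not ready by Day 15. This is a floor, because a success may still need oxygen. Only the last row is consistent with that.

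**Check with a different shape.** Half the patients are ready by Day 15 and the rest become ready uniformly over Days 16 to 90, censored at Day 70. Rejection is about 21 to 23% if all stay, about 14% if half stop early, 10 to 12% if three-quarters stop, and nominal if none are held. If only 20% fail and all stay, it rises to about 82 to 85%.

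**Anakinra against emapalumab.** With exponential R (median 15) and all ready patients held, the anakinra hazard ratio is 0.76 and the 90% interval falls wholly on the delay side in 21% of trials (nominal 5%). For emapalumab held to Day 13 the figures are 0.83 and 16%. With half held they are 0.89 and 12% against 0.92 and 8%.

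**Effect of removing the held days.** When R itself is analysed, the median hazard ratio is 0.98 to 1.02 and the delay-side rate is about 5 to 8%. This treats R as known exactly, not on the visit grid.

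**The case against.** A reader might infer that anakinra will appear to delay discharge. The documents do not support that. Nowhere do they say that recovered patients are kept in for infusions. SAP 8.2.1 and 8.5.1 foresee patients who stop before Day 15 because they have significantly improved, and Protocol 5.3.3.1 lets treatment end at the patient's wish. That improvement clause only scores the primary endpoint, so it does not correct the discharge analysis, but it does make complete holding unlikely.

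A reader might also take the upper rows of the table as the expected error. They require 67 to 90% of patients to be ready by Day 15, which conflicts with the plan's own 50% success rate. Nor is the bias simply proportional to compliance: full compliance does little harm when few patients recover before Day 15.

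Control patients may be held too. The schedule sets SpO₂ three times a day at Visits 1 to 6 in all arms, and Protocol 5.5.3.3 makes allowance for discharge only at Visit 7. If that kept controls in hospital, the difference between arms would shrink.

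Actual length of stay is a legitimate quantity in its own right and is an objective date, whereas category 6 is scored by unblinded staff. That stands as an argument against replacing the endpoint. Finally, Protocol 7.3.1 treats secondary p-values as exploratory, and the primary conclusion is untouched. That limits the weight of the point but does not remove it.

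**Conclusion.** The point holds conditionally. The definition counts treatment-schedule days as hospital stay, only the active arms can accrue them, and the SAP does not separate them. The direction is towards apparent delay, and the effect is larger for anakinra.

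Under the plan's 50% standard-of-care success rate and no drug effect, false rejection at a nominal 10% is roughly 20 to 23% if every ready anakinra patient stays to Day 15, about 14% if half stop early, and nominal if none are held. It becomes much larger only if most patients are ready well before Day 15. These figures rest on assumed readiness distributions, an assumed share held, and no deaths. The documents supply neither the readiness distribution nor the share held.

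**What to change.** Keep time to actual discharge as the protocol-named endpoint. In SAP 8.5.2 and 12.2.1:

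1. Add a pre-specified supportive Kaplan-Meier, log-rank and Cox analysis of time to first clinical status category 6 or 7. Use the same scheduled-visit grid in all three arms, so that an early discharge is timed at the next scheduled visit in every arm. Handle deaths in the same way in both analyses.
2. State, in the scoring instructions as well, that study-drug infusions alone do not count as ongoing medical care. Without this, a recovered patient on infusions could be scored category 5 and the same bias would return.
3. State that the discharge hazard ratio will be read alongside this analysis, because active-arm stay can include treatment-schedule days.

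The cost is SAP wording, a scoring note and one derived variable from data already collected. The downsides are open-label scoring and coarse timing: visits are about 3 days apart to Day 15 and then 13 days apart to Day 28 (28 − 15), which gives many ties. No change to treatment is proposed.

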5.5.3.8 Survival and hospital discharge

Data on survival and hospital discharge will be collected at Visits 7 (Day 28), Visit 8 and 9 (Weeks 6 and 10) and recorded in the CRF.

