5.5.5 Exploratory assessments

5.5.5.1 Clinical Status

Data on clinical status based on a 7-point ordinal scale will be collected at Visits 1 to 9 and recorded in the CRF.

The scale consists of the following categories:

- 1. Death
- 2. Hospitalized, requiring invasive mechanical ventilation or extracorporeal membrane oxygenation (ECMO)
- 3. Hospitalized, requiring non-invasive ventilation or high flow oxygen devices
- 4. Hospitalized, requiring supplemental oxygen
- 5. Hospitalized, not requiring supplemental oxygen requiring ongoing medical care
- 6. Hospitalized, not requiring supplemental oxygen no longer requires ongoing medical care
- 7. Not hospitalized

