7.3.3.2 Secondary endpoints supporting the primary objective

7.3.3.2.1 Time to mechanical ventilation and overall survival

Analysis of the time to mechanical ventilation from the point of randomization will be undertaken by plotting Kaplan-Meier curves for each of the 3 treatment groups and by pairwise comparisons (emapalumab/anakinra versus standard of care) using the logrank test. Hazard ratios will be estimated using the Cox proportional hazards model and these will be presented together with 90% two-sided confidence intervals. Overall survival (time to death from the point of randomization) and time to hospital discharge (from the point of randomization) will not be analysed at the end of Stage 2, but at the end of the follow-up period. This endpoint will be analysed as for time to mechanical ventilation.

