## **12.4 Exploratory endpoints**

### **12.4.1 Clinical status assessed by a 7-point ordinal scale**

Clinical status using the 7-point ordinal scale is an exploratory endpoint and the data collected will be summarized to show the number and percentage of patients in each category over time.

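### The planned Kaplan-Meier curve for time to hospital discharge censors deaths and so overstates the share discharged; cumulative incidence with death as a competing event should replace it

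*SAP*

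**What the plan says.** SAP 8.5.2 defines time to hospital discharge from randomization, with discharge as the only event. Patients not known to be discharged are censored at the last date on which the patient "was known to be hospitalized (e.g. date of visit, date of early discontinuation, or date of death"). Time to mechanical ventilation is treated alike: patients are censored at the last date they were known not to need "mechanical ventilation (e.g. date of Day 15 visit, date of early discontinuation, or date of death").

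SAP 12.2.1 says that time to mechanical ventilation is "undertaken by plotting Kaplan-Meier curves for each of the 3 treatment groups", with pairwise log-rank tests and Cox hazard ratios with 90% intervals. Of overall survival and discharge, which are analysed at the end of follow-up, it says "This endpoint will be analyzed as for time to mechanical ventilation". Protocol 7.3.3.2.1 agrees: "This endpoint will be analysed as for time to mechanical ventilation". The statistical methods part of the protocol synopsis names Kaplan-Meier curves for discharge directly.

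Neither document mentions competing risks or cumulative incidence, and neither keeps patients who die among those not yet discharged. The data for another approach are already planned: "Data on survival and hospital discharge will be collected at Visits 7 (Day 28), Visit 8 and 9 (Weeks 6 and 10"), under protocol 5.5.3.8.

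**The concern.** Censoring assumes that the censored patient could still have the event later, at the same rate as those who remain at risk. That is false for a patient who has died in hospital. Kaplan-Meier passes the dead patient's weight to the survivors, so one minus the curve rises above the proportion who actually left hospital.

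Deaths are foreseen: overall survival is an endpoint, and SAP 8.5.1 has a rule for patients who die by Day 15. A reader of the figure would conclude that more patients went home than did. The excess grows with mortality, so it differs between arms when mortality does, and a difference in discharge that comes from deaths is then partly hidden. SAP section 2 expects the planned analyses to be used in regulatory submissions and manuscripts.

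**Working it through.** The documents state no discharge share, event count or power for this endpoint, so there is no plan figure to reproduce. From the documents: 18 patients per arm (SAP section 6), about 70 days of follow-up (10 weeks, SAP 4.1), and the censoring rule of SAP 8.5.2. Assumed, because the documents are silent: mortality, timing of deaths and discharges, and the share still in hospital at the end.

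**Hand check, one arm of 18.** Suppose 2 deaths, 15 discharges and 1 patient still in hospital at Week 10. The true share discharged is 15/18 = 83.3%.
- If both deaths come first, 16 patients are at risk at the first discharge. The Kaplan-Meier product is 15/16 × 14/15 × … × 1/2 = 1/16, so one minus Kaplan-Meier is 93.8%.
- If both deaths follow the last discharge, the product is 17/18 × 16/17 × … × 3/4 = 3/18, which gives 83.3% and no bias.

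**All orders of deaths and discharges equally likely** (18 patients, 1 still in hospital):

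| Deaths | One minus Kaplan-Meier, mean (range) | True share |
|---|---|---|
| 1 | 93.3% (88.9 to 94.1) | 88.9% |
| 2 | 92.0% (83.3 to 93.8) | 83.3% |
| 3 | 90.4% (77.8 to 93.3) | 77.8% |
| 5 | 86.3% (66.7 to 92.3) | 66.7% |

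With 3 deaths the curve is too high in 99.9% of the orders.

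**Large sample.** Let m be mortality and s the share still in hospital at Day 70. Let F_d(t) and F_m(t) be the cumulative shares discharged and dead, with F_d(70) = 1 − m − s and F_m(70) = m. Discharge times follow a gamma distribution (shape 2, scale 9 days) and death times an exponential with mean 12 days, both truncated at Day 70. The true share is F_d(t). One minus Kaplan-Meier is 1 − exp(−∫ dF_d / (1 − F_d − F_m)).

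With s = 5%:

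| Mortality | Day 70: curve vs true | Excess, points | Day 28 excess, points |
|---|---|---|---|
| 5% | 94.4% vs 90% | 4.4 | 2.9 |
| 10% | 93.7% vs 85% | 8.7 | 5.7 |
| 20% | 92.0% vs 75% | 17.0 | 11.0 |
| 30% | about 89.5% vs 65% | about 24.5 | about 15.6 |

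With s = 10%, the excess is 4.0 to 21.4 points at Day 70 and 2.7 to 14.0 at Day 28.

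Constant hazards give a closed form and a similar answer. With s = 5%, one minus Kaplan-Meier at Day 70 is 1 − 0.05^(F_d/0.95). For 10% mortality that is 1 − 0.05^(0.85/0.95) = 93.1% against 85%. Over 5 to 30% mortality the excess is 4.1 to 22.1 points.

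**Difference between arms**, same model, same s in both arms:

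| Mortality | s | Mean time to death before truncation | Day | True gap, points | Gap on curves, points | Hidden |
|---|---|---|---|---|---|---|
| 10% vs 20% | 5% | 12 days | 70 | 10 | 1.7 | 83% |
| 10% vs 30% | 5% | 12 days | 70 | 20 | about 4.2 | about 79% |
| 10% vs 20% | 5% | 25 days | 28 | about 8 | about 5 | about 40% |
| 10% vs 30% | 20% | 25 days | 70 | 20 | 13.1 | 34% |

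Hidden is one minus the ratio of the two gaps.

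**Ventilation curve at Day 15.** With event times uniform to Day 15, v the share ventilated, u the share who die unventilated and F = v + u, one minus Kaplan-Meier is 1 − (1 − F)^(v/F). For v = 20%, u = 5% it is 20.6%, an excess of 0.6 points. For v = 50%, u = 10% it is 53.4%, an excess of 3.4 points. For 18 patients with 7 ventilated and 2 unventilated deaths, the mean over all orders is 41.7% against 38.9%. The excess of 2.8 points is half of one patient (1/18 = 5.6 points).

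**The case against.** The strongest reply is that this is one descriptive figure. Protocol 7.3.1 makes secondary endpoints descriptive and their p-values exploratory. The plan never says that the curve estimates the probability of discharge, and it schedules no Kaplan-Meier percentage at a landmark day. Overall survival is analysed at the same cut, so deaths are shown alongside. The 7-point scale also separates death from not hospitalized. Protocol 5.5.5.1 says: "Data on clinical status based on a 7-point ordinal scale will be collected at Visits 1 to 9 and recorded in the CRF". SAP 12.4.1 says that "the data collected will be summarized to show the number and percentage of patients in each category over time".

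Much of this stands, and it limits the importance of the point. SAP Table 2 lists only survival, discharge and adverse events at Weeks 6 and 10, and a reader might infer that the scale is dropped there. But Table 2 assigns time windows and does not cancel SAP 12.4.1. Even so, none of these outputs corrects the discharge curve, and its vertical axis will be read as a proportion of patients whatever the stated purpose.

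Three stronger readings are tempting and are not supported.
- A reader might infer that the log-rank tests and Cox hazard ratios are invalid. They are not: with deaths censored they compare cause-specific discharge rates. They do not describe the probability of discharge.
- A reader might infer that the curves would hide most of any difference in discharge due to deaths. That needs early deaths and few patients still in hospital. With later deaths, or more patients still in hospital, they hide about a third to two fifths.
- A reader might infer that the ventilation curves need the same mandatory change. The bias there is under one patient per arm at the assumed rates. The primary analysis already gives each arm's success proportion and counts deaths by Day 15 as failures.

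**Conclusion.** The point holds for the discharge curve. The direction follows from the censoring rule: the curve is too high as soon as one undischarged death precedes a later discharge, and it is unbiased if there is none. The size rests on assumed rates. It is about 4 to 25 points at Day 70 and 3 to 16 points at Day 28, for mortality of 5 to 30% with early deaths and 5% still in hospital. If mortality differs between arms, the curves hide from about a third to most of the resulting difference in discharge.

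The primary test, the stage decision rules, and the planned log-rank tests and hazard ratios are untouched. This is a correction that should be made to a secondary output, not a threat to the trial's main conclusion.

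**What to change.** Amend SAP 8.5.2 and 12.2.1. Align protocol 7.3.3.2.1 and the statistical methods part of the synopsis, which would otherwise still name Kaplan-Meier for discharge. Suggested text:

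*For time to hospital discharge, cumulative incidence will be plotted by treatment group, with death before discharge as a competing event, in place of Kaplan-Meier curves. The log-rank tests and Cox hazard ratios censor at death, are cause-specific, and will be read beside overall survival.*

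Keep Kaplan-Meier for overall survival. Making the same change to the curves for time to mechanical ventilation and time to IMV or ECMO would be consistent but is optional.

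The cost is a few sentences in the SAP and in two places in the protocol, plus minor programming. Survival and discharge are already collected, so no new data are needed. If nobody dies undischarged, the two curves coincide and nothing is lost.
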